#### **10.4 Visit 4: Day 15 (-2/+1 Days)**

- Concomitant medications
- AE assessment
- Vital signs
- Abbreviated physical examination
- Pre-dose spirometry
- Urine and blood samples collected for electrolytes
- Study drug administration
- Dispense study drug
- Collect unused study drug from previous visit
- Schedule the subject's Week 3 telephone call and review instructions if needed (Appendix 4, [Section 18.4](#))

#### **10.5 Day 22 ( $\pm$ 3 Days): Telephone Contact**

- Concomitant medications
- AE assessment
- Schedule the subject's next clinic visit and review instructions if needed (Appendix 4, [Section 18.4](#))

#### **10.6 Visit 5: Day 29 ( $\pm$ 2 Days) (Also the Early Termination Visit, If Applicable)**

- CFQ-R (not to be performed for subjects who discontinue early)
- Concomitant medications
- AE assessment
- Vital signs
- Weight and BMI
- Abbreviated physical examination
- Spirometry (the study drug will not be administered)
- 12-lead ECG
- Blood samples collected for hematology and serum chemistry tests, including electrolytes
- Blood sample collected for ADA testing
- Urine samples collected for electrolytes, urinalysis, and urine pregnancy test
- Urine pregnancy test performed
- Collect study nebulizer and unused study drug from previous visit
- Schedule the subject's follow-up telephone call

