e At Visit 2, spirometry including forced expiratory volume in 1 second (FEV1), percent predicted FEV1, forced vital capacity (FVC) and percent predicted FVC will be evaluated pre-dose, and postdose at 30 minutes, 2 hours, and 4 hours. At all other visits, only pre-dose spirometry will be performed.

f The CFQ-R will not be performed for subjects who are terminated early from the study

g See [Section 11.8](#) for specific laboratory tests to be performed.

h At Screening (Visit 1), a serum pregnancy test will be performed; at Visits 2 and 5, a urine pregnancy test will be performed.

i At Visit 2 only, the subject will be observed and monitored for at least 4 hours after completion of administration of the study drug. The subject may be discharged after 4 hours at the discretion of the Investigator (See [Section 10.2](#)).

j For Cohort 1 only, at Visit 2, blood samples for PK testing will be collected pre-dose and at 5±2 minutes and 15±3 minutes after completion of administration of the study drug.

Note: A subject may be re-screened once if they fail to meet randomization criteria for any reason. If this is the case, a new consent form must be signed, and a new screening number will be used.

**Table 3** shows the schedule and timing of events at Visit 2 (Randomization Visit; Day 1). The order of procedures in the table is the suggested approximate order in which the procedures should be carried out.

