#### 9.4.4 Withdrawal and Replacement of Subjects

##### 9.4.4.1 Criteria for Subject Withdrawal

In accordance with the Declaration of Helsinki (see Appendix 1, [Section 18.1](#)) and other applicable regulations, a subject has the right to withdraw from the study at any time and for any reason without prejudice to his or her future medical care by the physician or at the institution.

Subjects may also be withdrawn from the study for any of the following reasons:

- A female subject becomes pregnant (See [Section 12.6](#) for details on pregnancy reporting requirements)
- The Investigator may decide that the subject should be withdrawn. If this decision is made because of an intolerable AE or a clinically significant abnormality of a laboratory value, the study medication is to be discontinued and appropriate measures are to be taken. The Sponsor or Sponsor designee is to be notified immediately.
- The subject is unwilling to continue in the study.
- The Investigator stops participating in the study or the Sponsor, for any reason, stops the study.
- The subject or the Investigator decides it in the best interest of the subject to seek another treatment.
- The subject fails to return to the clinic for scheduled visits and does not respond to attempts at communication.

The reason for withdrawal will be recorded in the clinical records and the electronic case report form (eCRF). All subjects who prematurely discontinue the study treatment will undergo an early termination visit (see [Section 10.6](#)). Subjects who are withdrawn from the study will not be replaced. All subjects who are withdrawn or discontinue should be offered other approved medical care.

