#### *9.4.4.2 Evaluations at Withdrawal*

For any subject who is withdrawn before completing all study visits, the Investigator should:

- Perform the procedures included in the early termination visit (see [Section 10.6](#))  
These assessments should be performed as soon as possible after the last administration of the study drug, but in any case, will be performed no later than 14 days after withdrawal or discontinuation of the study treatment.
- Complete all appropriate eCRF pages, providing the date of and explanation for the subject's withdrawal/discontinuation.
- When indicated, arrange for appropriate medical follow-up care for the discontinued subject.

If the subject fails to attend the scheduled early termination visit, the Investigator or designee will make at least 2 attempts to contact the subject by telephone. If the subject does not respond, s/he will be considered lost to follow up.

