## 11. METHODS OF ASSESSMENT

### 11.1 Cystic Fibrosis Questionnaire - Revised

At the Randomization Visit and at Week 4 (Visit 5) subjects will complete the respiratory and physical domains of the CFQ-R, and the Investigator or designee will record the data in the appropriate eCRF.

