##### CFQ-R

The change from baseline in CFQ-R respiratory domain and physical domain at Week 4 will be summarized and compared between the treatment groups and the placebo.

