## 7.2 Secondary Efficacy Variables

- Change from baseline in ppFEV1 at visits 3 and 4 (weeks 1 and 2)
- Change from baseline in FEV1 at visits 3, 4 and 5
- Change from baseline in forced vital capacity (FVC) and percent predicted FVC (ppFVC) at visits 3, 4 and 5
- Change from baseline in 25-75% forced expiratory Flow (FEF25-75) at visits 3, 4 and 5
- Change from baseline in Cystic Fibrosis Questionnaire-Revised (CFQ-R) (respiratory and physical domains) at visit 5.

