### Cystic Fibrosis Questionnaire – Revised (CFQ-R) Domain Scores

The recall period for this instrument is within the past 2 weeks. The domain scores are calculated as follows, as per University of Miami’s scoring guidelines:

First, item scores are assigned as values between 1 and 4. Next, items #6, #10, #13, #15, #17, #18, #23, #28, #30, #32, #34, #35, and #43 are reverse scored, where the new score is (5 – old score). If an item response is missing, the median value of scores for other items within that domain (e.g., #1 - #5, #13, #19, #20 for physical domain, and #40 – #42, #44 – #46 for respiratory domain) will be imputed, if no more than half of the responses for that domain are

Sponsor: SPYRYX Biosciences

Protocol no: SPX-101-CF-201

---

missing. If more than half of the answers for a specific domain are missing, that domain score will be missing.

The respiratory domain score is calculated as (#40 + #41 + #42 + #44 + #45 + #46 – 6)/18 \* 100. The physical domain score is calculated as (#1 + #2 + #3 + #4 + #5 + #13 + #19 + #20 – 8)/24 \* 100.

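### CFQ-R is left out of the early-termination visit, so the only patient-reported secondary endpoint is in effect a completers-only result

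*Protocol*

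**What the plan says.** **Collection.** Protocol Section 11.1 sets two time points: "At the Randomization Visit and at Week 4 (Visit 5) subjects will complete the respiratory and physical domains of the CFQ-R". Visit 5 is also the early-termination visit, and Section 10.6 carves the questionnaire out of it: "CFQ-R (not to be performed for subjects who discontinue early". Footnote f to Table 2 in Protocol Section 9.1 agrees: "The CFQ-R will not be performed for subjects who are terminated early from the study". Footnote f to Table 1 in the SAP repeats this. Spirometry, ECG, hematology and chemistry, urine tests and the antidrug-antibody sample all stay in the Section 10.6 list.

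**Who is affected.** Protocol Section 9.4.4.1 routes everyone who stops treatment to that visit: "All subjects who prematurely discontinue the study treatment will undergo an early termination visit". Section 9.4.4.2 sets its outer limit: the assessments "will be performed no later than 14 days after withdrawal or discontinuation of the study treatment".

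**Endpoint and analysis.** SAP Section 7.2 lists as secondary "Change from baseline in Cystic Fibrosis Questionnaire-Revised (CFQ-R) (respiratory and physical domains) at visit 5"; every other secondary variable is spirometric. Protocol Section 13.6.4.2 says the two domains "at Week 4 will be summarized and compared between the treatment groups and the placebo". SAP Section 12.6.2 plans only a summary and a listing, with no model or test.

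**Missing scores.** SAP Section 8.0 excludes subjects with no change score. CFQ-R imputation is at item level only, and a domain with more than half its answers absent stays missing (SAP Sections 8.0 and 12.6.5). Multiple imputation and the repeated-measures model cover ppFEV1 only. ITT is the named set for efficacy (SAP Sections 9.1 and 12.6).

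**The concern.** A subject who stops treatment early still attends a clinic visit at which nearly everything else planned for Visit 5 is done, but is not asked about symptoms or physical functioning on the CFQ-R. With no score between Visits 2 and 5, that subject has no post-baseline CFQ-R at all. The tables would carry an ITT label but describe only those who reached Visit 5 on study.

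This matters because leaving may be related to what the questionnaire measures. Protocol Section 10.2.2 foresees withdrawal after bronchospasm, and in Cohort 1 respiratory adverse events were reported in 35.7% of placebo, 53.3% of 60 mg and 43.8% of 120 mg subjects (Protocol Section 7.3.2). If people leave because their breathing has worsened, the remaining scores describe a selected group, and the report will hold no patient-reported data from those who left.

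**Working it through.** **1. Is there a stated figure to reproduce?** Not for the CFQ-R: neither document gives a sample size, effect, SD or expected missing rate for it. The only Cohort 2 design figure is ppFEV1 power of 88% to 97% (N = 45, 2:1, difference 6 to 8, SD 7.58, one-sided alpha 0.10). It reproduces closely, at 88.4% and 97.8% with the noncentral t on 43 degrees of freedom, and has no bearing on this point.

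**2. Can anyone who leaves early contribute a CFQ-R change score?** Stopping treatment leads to the early-termination visit, where the CFQ-R is not given. There is no interim score, whole-questionnaire gaps are not imputed, and subjects without a change score are excluded. The answer is no. SAP Section 8.0 defines a completer as someone not terminated early who completes Visit 5, so the CFQ-R set is drawn from completers only.

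**3. How does spirometry differ?** SAP Section 8.0 maps any assessment on Study Day 22 or later to Week 4. A subject who stops on Day 12 and is seen on Day 24 is within the 14-day limit and can enter the primary ppFEV1 analysis, but has no CFQ-R. A subject seen before Day 22 has no Week 4 value for either endpoint.

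**4. How many might be missing?** Protocol Section 7.3.2 gives 45 treated and 40 completing in Cohort 1.

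- Of treated: (45 − 40)/45 = 5/45 = 11.1%.
- Of the 46 randomized: (46 − 40)/46 = 6/46 = 13.0%. This counts one subject who, on the protocol's figures, was not treated, so 11.1% is the better guide to losses during treatment.
- Carried to Cohort 2: 45 × 5/45 = 5 missing and 40 analysed, out of 30 active and 15 placebo.

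The expectation of minimal attrition stands in the Cohort 1 paragraph of Protocol Section 13.2; the Cohort 2 paragraph makes no allowance for attrition.

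**5. What could that do to the difference?** Let leavers' mean change be D points worse than completers' in the same arm, with the same D in both arms. An arm's mean over all its subjects is then its completer mean minus (share missing × D). The completers-only difference, active minus placebo, departs from the all-subject difference by

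shift = D × (k_A/30 − k_P/15),

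where k_A and k_P are the numbers missing on active and placebo. D is an assumption; the documents give nothing to set it. A positive shift flatters SPX-101.

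| Missing, active / placebo | D = 5 | D = 10 | D = 20 |
|---|---|---|---|
| 5 / 0 | +0.8 | +1.7 | +3.3 |
| 4 / 1 | +0.3 | +0.7 | +1.3 |
| 3.33 / 1.67 (proportional to 2:1) | 0 | 0 | 0 |
| 0 / 5 | −1.7 | −3.3 | −6.7 |

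For example, 10 × (5/30 − 0/15) = +1.67 and 10 × (0/30 − 5/15) = −3.33. The sign depends entirely on how the losses split between arms, which the documents do not report.

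**The case against.** **No decision rests on the CFQ-R.** The success rule in SAP Section 12.6.1 uses ppFEV1 alone, and the SAP only summarises the questionnaire. This stands and limits the weight of the point. It does not remove it: a summary that leaves out those who stopped is still a completers-only summary, and the protocol does plan a comparison with placebo.

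**The bias may not favour active treatment.** A reader might infer that the omission flatters SPX-101, because intolerant subjects vanish from its arm. The documents do not support that. They report neither the arm nor the reason for the Cohort 1 non-completers. The cough signal was mainly at 60 mg (26.7%), a dose not used in Cohort 2, against 6.3% at 120 mg. One 120 mg subject did have serious cough and dyspnea, so symptom-related departure is plausible, but its balance between arms is unknown.

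**The loss is not beyond repair in analysis.** A reader might also infer that nothing can be done afterwards. Baseline CFQ-R, spirometry, adverse events and withdrawal reasons are collected, and delta-adjusted, reference-based or worst-case sensitivity analyses need no interim score. Such analyses would still rest on assumptions about the missing scores that the trial cannot check.

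**Termination scores are hard to interpret.** The SAP says "The recall period for this instrument is within the past 2 weeks". A score taken 14 days after the last dose covers an off-treatment period; one taken on Day 5 covers about 10 days (14 − 4) before the first dose. This may be why the questionnaire was left out, though no reason is given. It argues for a supportive role for these scores, not against collecting them.

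**Conclusion.** The point holds as a gap in data collection. The exclusion appears in three places that agree with one another, and no planned analysis makes up for it. At the Cohort 1 rate of 11.1% of treated subjects, about 5 of the 45 Cohort 2 subjects would have no post-baseline CFQ-R.

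Neither the direction nor the size of a resulting bias can be stated. With an assumed 10-point gap, equal in both arms, the shift ranges from −3.3 to +1.7 points; with gaps of 5 to 20 points, the extremes run from −6.7 to +3.3. These figures also assume that Cohort 2 loses subjects at the Cohort 1 rate.

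It would also be too much to conclude that giving the CFQ-R at termination turns the endpoint into a Week 4 ITT comparison. Visit timing, the recall period and non-attendance all prevent that. What it provides is observed information on people about whom the CFQ-R would otherwise say nothing. For a secondary endpoint on which no success rule depends, this is an inexpensive improvement worth making, not a threat to the trial's main conclusion.

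**What to change.** 1. Delete the exclusion in Protocol Section 10.6, Protocol Table 2 footnote f and SAP Table 1 footnote f, and give the respiratory and physical domains at the early-termination visit.
2. Keep the scheduled Visit 5 analysis as the main one.
3. Add a supportive summary that includes termination scores, showing days since last dose and study day for each.
4. Report the number with missing CFQ-R by arm and by reason for discontinuation.
5. In the same revision, reconcile the protocol's planned comparison with placebo and the SAP's summary-only plan.

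**Cost.** The two domains have 14 items (8 physical and 6 respiratory, from the scoring rules in SAP Section 8.0), given at a visit that already takes place. The rest is a short protocol amendment, a SAP edit and one or two extra tables. The downside is that termination scores arrive at varying times and may partly reflect off-treatment or pre-treatment days, so they must stay supportive. If Cohort 2 collection has already ended, step 1 is no longer possible; the reporting in step 4 remains, and a sensitivity analysis with stated assumptions could take the place of step 3.

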**10.7 Follow-up Telephone Call: Day 31 ( $\pm$  1 Day)**

- Concomitant medications
- AE assessment

## 11. METHODS OF ASSESSMENT

### 11.1 Cystic Fibrosis Questionnaire - Revised

At the Randomization Visit and at Week 4 (Visit 5) subjects will complete the respiratory and physical domains of the CFQ-R, and the Investigator or designee will record the data in the appropriate eCRF.

### 11.2 Pregnancy Testing

Subjects who are pregnant will be excluded from the study. At the screening visit (Visit 1), blood will be collected for a serum pregnancy test. At the randomization visit (Visit 2) and at Visit 5, a urine pregnancy test will be performed. For more information about pregnancy-related procedures and reporting, see [Section 12.6](#).

### 11.3 Pulmonary Function Tests

Spirometry will be performed at all clinic visits using equipment provided by the centralized spirometry vendor, Biomedical Systems (BMS). Spirometry will be performed in accordance with ATS/ERS guidelines and the GLI predictors of spirometric lung volume normal ranges [2; 3]. At Visit 2, spirometry will be performed pre-dose, and postdose at 30 minutes, 2 hours, and 4 hours postdose after completion of administration of the study drug. At all other visits, only pre-dose spirometry will be performed. The following parameters will be recorded:

- Absolute FEV1 and ppFEV1
- Absolute FVC and ppFVC

### 11.4 Vital Signs and Weight

Systolic blood pressure and diastolic blood pressure will be measured on the same arm (preferentially on the left arm) after the subject has been in a supine/sitting position for 5 minutes. The heart rate will be recorded simultaneously with blood pressure measurements. The body temperature will also be recorded. On the first day of dosing, vital signs will be measured pre-dose, at 30 minutes and 1, 2, and 4 hours postdose.

Body weight (kg) will be measured without shoes or jacket. Height will be measured at the Screening Visit to assess BMI.

During the study, the measurement of vital signs may be repeated at the discretion of the Investigator for safety reasons. Clinically relevant abnormal findings will be reported as AEs.

### 11.5 Physical Examination

Physical examinations will be performed by a physician or qualified designee and will include examination of the following: general appearance, head, ears, eyes, nose, throat (HEENT), neck, skin, cardiovascular system, respiratory system, abdomen, and nervous system (including a neurological examination; with an assessment of the reflexes, motor and sensory nerve assessment, sensory checks [extremities] and mental status assessment). At all visits after the Screening visit, the Investigator or qualified designee may perform an abbreviated physical examination, defined as a review of HEENT, neck, respiratory system, cardiovascular system, and the skin.

For each body system, the Investigator will document any abnormalities and will provide an assessment of normal or abnormal on the eCRF.

### **11.6    Electrocardiogram**

Computerized 12-lead ECG recordings will be obtained, after the subject has been supine for 5 minutes. Each lead will be recorded for at least 3-5 beats at a speed of 25 mm/sec paper speed and 10 mm/mV amplitude. At a minimum, heart rate and the P, PR, QRS, QT, and QTcF intervals will be obtained and entered into the eCRF. The Investigator will also evaluate whether the ECG is normal or abnormal, and if abnormal, whether the abnormality is clinically significant. A copy of all ECGs will be retained on site and may be collected for central review if required (ie, in case emerging ECG data necessitate expert evaluation).

An ECG may be repeated for quality reasons and additional ECGs may be collected by the Investigator for safety reasons. Any clinically relevant abnormal findings noted at Screening will be exclusionary. Any clinically relevant abnormal findings after the first dose of the study drug will be reported as AEs. Subjects with clinically relevant cardiovascular AEs (or clinically relevant ECG changes) must be withdrawn from the study (see [Section 9.4.4](#)).

### **11.7    Adverse Events and Pulmonary Exacerbation**

At each clinic visit, the Investigator or designee will ask the subject about any symptoms experienced since the previous contact to assess for AEs. The Investigator will also assess whether the subject had a pulmonary exacerbation since the previous visit, and if so, record it in the eCRF, complete the pulmonary exacerbation eCRF, and follow all procedures for reporting an AE or SAE. See Appendix 3, [Section 18.3](#) for the Fuchs 1996 criteria for pulmonary exacerbation.

On the first day of dosing, AEs will be assessed pre-dose, at 30 minutes, and 1, 2, and 4 hours postdose.

### **11.8    Clinical Laboratory Testing**

Venous blood samples and urine samples will be collected for hematology and chemistry testing at study visits as outlined in [Section 10](#).

- **Hematology:** White blood cell count, red blood cell count, red blood cell indices, hemoglobin, hematocrit, platelet count, and a 5-part white blood cell differential (neutrophils, lymphocytes, monocytes, eosinophils, and basophils)
- **Clinical chemistry:** Liver function tests (ALT, ALP, AST, and gamma glutamyltranspeptidase), electrolytes (sodium, potassium, chloride, and bicarbonate), total bilirubin, blood urea nitrogen, calcium, C-reactive protein, creatinine, glucose, lactate dehydrogenase, total protein, and albumin
- **Blood electrolytes:** sodium, potassium, chloride, and bicarbonate
- **Urine electrolytes:** sodium, potassium, and chloride
- **Urinalysis:** pH, specific gravity, protein, glucose, and ketones

Routine laboratory tests will be performed by Eurofins Central Laboratories. Details about the procedures to be followed for sample collection, storage, and shipment will be provided in a Laboratory Manual.

Additional and repeat laboratory testing may be performed at the discretion of the Investigator.

#### **11.9 Blood Samples for Pharmacokinetic Testing (Cohort 1 Only)**

At Visit 2 only, venous blood samples were collected pre-dose and at  $5 \pm 2$  minutes and  $15 \pm 3$  minutes after completion of administration of the study drug. Pharmacokinetic testing will be performed by QPS. Details about the procedures to be followed for sample collection, handling, storage, and shipment will be provided in a Laboratory Manual.

#### **11.10 Blood Samples for Antidrug Antibody Testing**

At Visit 5 only, a venous blood sample will be collected for ADA testing, which will be performed by QPS. Details about the procedures to be followed for sample collection, handling, storage, and shipment will be provided in a Laboratory Manual.

## 12. SAFETY MEASUREMENTS AND VARIABLES

### 12.1 Adverse Events

The definitions and reporting procedures provided in this protocol comply with the current CFR 21 Part 312. An AE is any untoward medical occurrence or worsening of a pre-existing condition, regardless of its relationship to the investigational medicinal product. An AE can therefore be any unfavorable or unintended sign, including an abnormal laboratory finding, symptom, or disease temporally associated with the use of an investigational medicinal product whether or not considered related to the product. Adverse events that are reported after signing the informed consent but prior to randomization, will be recorded in medical history. Adverse events that are reported after initiation of treatment up until the final study visit phone call on Day 31 will be considered TEAEs. Serious adverse events occurring at any time from informed consent to 28 days after the last dose of treatment with study drug will be reported. Subjects will be monitored for AEs throughout the entire study.

Investigators will ask the subject at each visit if they have experienced any untoward effects since the last study visit. The Investigator or designee will record the following information about AEs on the eCRFs: an AE term or description of the event, severity, event start date, event end date (if known), any action (eg, treatment and follow-up tests), the outcome of the event, and the Investigator's assessment of the relationship to the study treatment.

Even if the Investigator feels there is no relationship to the study drug, all AEs must be recorded in the eCRF.

